6.4.7. Cumulative Proportion of Responders Analysis

- total cumulative distribution of percent reduction ($\geq 0\%$, $\geq 10\%$, $\geq 20\%$, $\geq 30\%$, $\geq 40\%$, $\geq 50\%$, $\geq 60\%$, $\geq 70\%$, or $\geq 80\%$) from baseline (run-in period) in the monthly average number of CH attacks during the 12-week period after the first dose of the IMP, ie, based on week 0 to 12 data

- cumulative distribution function plot of percent reduction ($\geq 0\%$, $\geq 10\%$, $\geq 20\%$, $\geq 30\%$, $\geq 40\%$, $\geq 50\%$, $\geq 60\%$, $\geq 70\%$, or $\geq 80\%$) from baseline (run-in period) in the monthly average number of CH attacks during the 12-week period after the first dose of the IMP, ie, based on week 0 to 12 data

The 12-week period is the period from administration of the first dose of the IMP to the EOT/early withdrawal visit. CH attacks within the 12-week period will be derived from the e-diary data as described in Section 6.1.1 and prorated to 28. Missing data handling methods are provided in Section 6.1.4.2. The percentage of reduction from baseline will be calculated using formula [2].

A cumulative proportion of responder’s analysis (CPRA) will be provided for the percent reduction from baseline in the monthly average number of CH attacks during the 12-week period. This technique is a special case of the empirical cumulative distribution function, which requires that the data be specified as the cumulative proportion of patients who have values above all specified cut-off values of interest (0%, 10%, 20%, 30%, 40%, 50%, 60%, 70%, or 80%).

Let Y_{ki} denote the percent reduction from baseline in the monthly average number of CH attacks during the 12-week period for patient i in treatment group k , where $k = 1,2,3$ and $i = 1, \dots, n_k$, n_k is the total number of patients in treatment group k .

Let C_j denote the j^{th} cut-off value of interest, where $j = 1, \dots, J$. For the cut-off value ranges from 0% to 80% by 10, $C_1 = 0, C_2 = 10, \dots, C_9 = 80$.

The cumulative proportion of responders will be calculated as follows:

$$P_{kj} = \frac{1}{n_k} \sum_{i=1}^{n_k} I(Y_{ki} \geq C_j),$$

where

$$I(Y_{ki} > C_j) = \begin{cases} 1, & \text{if } Y_{ki} \geq C_j \\ 0, & \text{if } Y_{ki} < C_j \text{ or if } Y_{ki} \text{ is missing} \end{cases}$$

Summary statistics for total cumulative reduction at $\geq 0\%$, $\geq 10\%$, $\geq 20\%$, $\geq 30\%$, $\geq 40\%$, $\geq 50\%$, $\geq 60\%$, $\geq 70\%$, or $\geq 80\%$ will be presented.

The CPRA graph will place responder levels of interest (0%, 10%, 20%, 30%, 40%, 50%, 60%, 70%, or 80%) on the x-axis and graph the associated proportion of patients calculated for that response level on the y-axis for each treatment group. A 2-dimensional graph will display data by plotting P_{kj} (y-axis) verse C_j (x-axis), with k overlaid curves representing k treatment groups.

6.4.8. Mean Change from Baseline in the Monthly Average Number of CH Attacks of at Least Severe Severity During the 12-Week Period After Administration of the First Dose of the IMP

The mean change from baseline in the monthly average number of CH attacks of at least severity will be analyzed using an ANCOVA in a manner analogous to the endpoints in Section 6.2.2.

The derivation of input data for this analysis is the same as the primary analysis except only counting CH attacks with severity of severe or very severe.

6.4.9. Changes from Baseline in Responses to Questionnaires That Measure Quality of Life, Satisfaction with Treatment, and Health Status

These will include analyses based on the quality of life, satisfaction with treatment, and health status measured by the EQ-5D questionnaire, HADS, SF-12, Impact on Partner and Family questionnaire, WPAI questionnaire, and PGIC scale.

6.4.9.1. Change from Baseline in EuroQol-5 Dimension Questionnaire

The 5-level EQ-5D questionnaire ([Appendix C](#)) is a standardized questionnaire that assesses overall state of health. The EQ-5D questionnaire consists of 2 parts. In part 1, patients will rate their health in 5 domains: mobility, self-care, usual activities, pain/discomfort, and anxiety/depression using a scale of 1 to 5 as follows:

1=no problems

2=slight problems

3=moderate problems

4=severe problems

5= extreme or unable to

In part 2, patients will rate their health state on a 0 to 100 mm visual analog scale; a rating of 0 means the worst imaginable health state, and a rating of 100 means the best imaginable health state. Data will be collected in the investigational site tablet at visit 2, 3, and 5.

Part 1 data will be summarized using descriptive statistics by domain and visit. A missing category will be presented if applicable.

For part 2 data, change from baseline at visit 3 and 5 in the health status (visual analog scale) will be analyzed using an MMRM in a manner analogous to the analysis as described in Section 6.2.3.2. Postbaseline data will include data from visits 3 and 5. Results from overall and each visit will be presented.

6.4.9.2. Hospital Anxiety and Depression Scale

The HADS is a 14-item scale developed to measure anxiety (7 items) and depression (7 items). Each item is scored on a 4-point scale from 0 to 3. Total scores for depression and anxiety range from 0 to 21; a total score of 0 to 7 is normal, 8 to 10 is borderline abnormal, and 11 to 21 is abnormal. Scoring details are provided in [Appendix D](#).

Patients will complete the HADS in the investigational site tablet at visits 2, 3, and 5. Total score for each sub-scale (depression or anxiety) will be calculated by summation of raw scores from the 7 items for each sub-scale. Categorical score level (normal, borderline abnormal, and abnormal) will be derived accordingly based on the total scores for each sub-scale.

For total score calculations of each sub-scale, missing score(s) will be handled as follows:

- If having scores for at least 4 items, the missing score will be inferred using the mean score of the remaining items for the patient. The total score for the sub-scale will be calculated as follows:

$$\frac{\sum \text{scores from } N \text{ items}}{N} \times 7$$

Where N (≤ 7 and ≥ 4) is the number of non-missing items for a sub-scale.

- If missing score for more than 4 items, the total score for that sub-scale will be invalid (missing).

Change from baseline at visits 3 and 5 in total score for each sub-scale (depression and anxiety) will be analyzed using an MMRM in a manner analogous to the analysis as described in Section 6.2.3.2. Postbaseline data will include data from visits 3 and 5. Results from overall and each visit will be presented.

Raw data and total scores for each sub-scale (depression and anxiety; numerical and categorical level) will also be summarized using descriptive statistics by visit. A missing category will be presented if applicable.

For summaries with the total scores, a footnote will be added indicating 0-7 = Normal; 8-10 = Borderline abnormal; 11-21 = Abnormal.

6.4.9.3. 12-Item Short-Form Health Survey

The 12-Item Short-Form Health Survey version 2 (SF-12v2) is a generic health survey containing 12 items (questions) to measure functional health and well-being rated in 8 health domains:

- general health (1 item)
- physical functioning (2 items)
- role functioning - physical (2 items)
- role functioning - emotional (2 items)
- bodily pain (1 item)
- mental health (2 items)
- vitality (1 item)
- social functioning (1 item)

Detail descriptions of each item are provided in [Appendix E](#). Patients will complete the SF-12 in the investigational site tablet at visits 2, 3 and 5.

Physical Composite Scores (PCS-12) and Mental Health Composite Scores (MCS-12) will be computed using scoring software ([Scoring Software v5.0](#)).

Change from baseline at visits 3 and 5 in PCS-12 and MCS-12 will be analyzed using an MMRM in a manner analogous to the analysis as described in Section 6.2.3.2. Postbaseline data will include data from visits 3 and 5. Results from overall and each visit will be presented.

Raw data will be summarized using descriptive statistics by visit.

6.4.9.4. Impact on Partner and Family Questionnaire

The patients and partners/family members of patients participating in the study, if applicable, will complete an Impact on Partner and Family questionnaire at visits 2, 3, and 5. Responses will be recorded in the investigational site tablet. The questionnaire for patients is provided in [Appendix F](#); for partners in [Appendix G](#).

Patients and partners/family members of patients will respond the questions based on impact of CH “during the last 12 weeks” at baseline visit and impact of CH “since last assessment” at postbaseline visits.

Raw data will be summarized using descriptive statistics.

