### **6.6. Impact on Partner and Family Questionnaire**

The partners/family members of patients participating in the study, if applicable, will complete an Impact on Partner and Family questionnaire at the time points detailed in [Table 2](#). Responses will be recorded in the investigational site tablet. The questionnaire will include questions about the impact of CH on the patient's ability to do chores, the number of days that the patient missed a family or social activity since the last assessment due to CH, and the frequency with which the patient avoids making plans for family/social activities due to CH. Partners/family members will

be asked to attend the study visit with the patient or to return to the investigational center within  $\pm 3$  days of the patient's visit if unable to appear at the same time.

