#### **Visit 3 (Week 4 [Day 28+3 Days])**

The following predose procedures and assessments will be performed at visit 3:

- Review study compliance.
- Review electronic diary data.
- Perform vital signs measurements (includes systolic and diastolic blood pressure, pulse, and body temperature).
- Inquire about adverse events.
- Inquire about concomitant medications.
- Perform clinical laboratory tests (serum chemistry, hematology, coagulation, and urinalysis).
- Perform urine  $\beta$ -HCG pregnancy test (for women of childbearing potential only).
- Obtain a 4-mL blood sample for pharmacokinetics analysis from either arm.
- Obtain a 5-mL blood sample for ADA analysis.
- Administer the HADS, EQ-5D questionnaire, SF-12, and WPAI questionnaire.

- Each patient’s partner/family member completes the Impact on Partner and Family questionnaire. Partners/family members will be asked to attend the study visit with the patient. Partners/family members will be asked to attend the study visit with the patient or to return to the investigational center within  $\pm 3$  days of the patient’s visit if unable to appear at the same time.
- Complete the PPSI.
- Complete the PGIC scale.
- Complete the eC-SSRS Since Last Visit version.
- Perform wearable sensor device check and compliance check for patients enrolled in the wearable sensor substudy.

In addition, a 6-mL blood sample for pharmacogenomic analysis (DNA) may be obtained at this visit if the sample is not obtained at visit 2 (week 0), unless the patient declines or local regulations prohibit pharmacogenomic testing.

After completing predose assessments, patients will be treated with IMP. Refer to Section 5.1.1.1 for details regarding IMP administration.

The following procedures and assessments will be performed at visit 3 (week 4) after dosing:

- Perform local injection site assessment immediately (+10 minutes) and at 1 hour ( $\pm 15$  min) after completing IMP administration. Additional injection site assessments may be performed based on the severity of any observed injection site reaction. See Section 7.11 for additional details.
- Evaluate for anaphylaxis and hypersensitivity reactions.
- Inquire about postdose adverse events before the patient leaves the study center.

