#### **End-of-Treatment Visit (Visit 5 [Week 12 (Day 84+3 Days)]/Early Withdrawal Visit**

The following procedures and assessments will be performed at the EOT visit (visit 5)/early withdrawal visit:

- Review electronic diary data
- Review study compliance.
- Perform triplicate 12-lead ECGs.
- Perform vital signs measurements (includes systolic and diastolic blood pressure, pulse, and body temperature).
- Perform a physical examination (including weight).
- Inquire about adverse events.
- Inquire about concomitant medications.
- Perform clinical laboratory tests (serum chemistry, hematology, coagulation, and urinalysis).
- Perform a serum  $\beta$ -HCG pregnancy test (for women of childbearing potential only).
- Obtain a 4-mL blood sample for pharmacokinetics analysis from either arm.
- Obtain a 5-mL blood sample for ADA analysis.
- Obtain blood sample for biomarker analysis (8.5-mL serum, 6 mL plasma, and 2.5 mL for ribonucleic acid [RNA]).
- Obtain a 5-mL urine sample for biomarker analysis.
- Administer the HADS, EQ-5D questionnaire, SF-12, and WPAI questionnaire.

- Each patient’s partner/family member completes the Impact on Partner and Family questionnaire. Partners/family members will be asked to attend the study visit with the patient. Partners/family members will be asked to attend the study visit with the patient or to return to the investigational center within  $\pm 3$  days of the patient’s visit if unable to appear at the same time.
- Complete the PPSI.
- Complete the PGIC scale.
- Complete the eC-SSRS Since Last Visit version.
- Perform wearable sensor device check and compliance check for patients enrolled in the wearable sensor substudy.

In addition, a 6-mL blood sample for pharmacogenomic analysis (DNA) will be obtained at this visit if the sample is not obtained at an earlier visit, unless the patient declines or local regulations prohibit pharmacogenomic testing.

Patients enrolling into Study TV48125-CNS-30058 for the purpose of evaluating the long-term safety of fremanezumab on the same day as this visit will keep the electronic diary device. All other patients will return the electronic diary device after completing this visit.

Patients in the wearable device substudy will return the wearable sensor if they do not rollover into the long-term safety study (Study TV-48125-CNS-30058) or if they rollover into the long-term safety study but do not wish to continue participating in the wearable sensor substudy.

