- mean change from baseline (run-in period) in the monthly average number of CH attacks of at least severe severity during the 12-week period after administration of the first dose of the IMP, ie, based on week 0 to 12 data
- changes from baseline (day 0) in responses to questionnaires that measure quality of life, satisfaction with treatment, and health status
- the relationship between biofluid biomarkers and fremanezumab concentrations
- the relationship between specific genetic polymorphisms within the calcitonin gene-related peptide (CGRP) receptor-ligand complex and headache-associated genes versus headache response, specific CH attack clinical features (eg, severity, IMP effects, IMP efficacy), and/or safety (eg, adverse events to IMP)
- the relationship between baseline levels and/or mean changes in levels from baseline (day 0) in biofluid biomarkers versus treatment, CH response status (onset/duration), and response status (ie, responders versus nonresponders)

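### The missed-days item of the Impact on Partner and Family questionnaire is recalled over about 12, 4 and 8 weeks at its three visits, so the planned raw summary cannot show change from baseline for that item.

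*SAP*

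**What the plan says.** SAP 6.4.9.4 fixes two recall periods. At visit 2, "Patients and partners/family members of patients will respond the questions based on impact of CH “during the last 12 weeks” at baseline visit"; later, respondents report "impact of CH “since last assessment” at postbaseline visits". The same section says that patients and their partners or family members "will complete an Impact on Partner and Family questionnaire at visits 2, 3, and 5". Protocol Table 2 agrees, and the visit 4 procedures in protocol Appendix B do not include the questionnaire.

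Protocol 6.6 describes the content in three parts: ability to do chores, how often plans are avoided, and "the number of days that the patient missed a family or social activity since the last assessment due to CH". The third part is a count. Protocol 6.6 does not mention a 12-week period at baseline; that appears only in the SAP.

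The whole analysis in SAP 6.4.9.4 is this: "Raw data will be summarized using descriptive statistics". The endpoint it serves, in SAP 1.5, is "changes from baseline (day 0) in responses to questionnaires that measure quality of life, satisfaction with treatment, and health status", and SAP 6.4.9 lists this questionnaire under that endpoint.

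**The concern.** A count of days grows with the period over which it is counted. Here the period shrinks to about a third of its baseline length at visit 3 and then doubles for visit 5. If the raw counts are tabulated by visit, the means move between columns even when the disease does not, and a real change from baseline cannot be separated from the change in recall period.

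Elsewhere the SAP takes care over this. SAP 6.1.2 prorates attack counts and medication-use days to 28 or 7 days, and SAP 6.1.3 does so even where a 4-week window misses 28 days by only a few days. No such step is given here, where the periods differ threefold.

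At stake is the readability of one exploratory item, within each arm and over time.

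**Working it through.** The plan gives no figure of its own to reproduce on this point.

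**Inputs**
- Baseline recall: 12 weeks, or 84 days (SAP 6.4.9.4).
- Visit 3: day 28 ±3 (protocol Table 2). Recall since visit 2 is about 28 days.
- Visit 5: day 84 ±3 (protocol Table 2). The questionnaire is not given at visit 4, so recall since visit 3 is about 84 - 28 = 56 days.
- Rate of missed days: the documents give none. I assume a constant r days per week and show a range.

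**Expected raw count** = r × recall in weeks.

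| r (days/week) | Visit 2 (12 weeks) | Visit 3 (4 weeks) | Visit 5 (8 weeks) |
|---|---|---|---|
| 0.5 | 6 | 2 | 4 |
| 1 | 12 | 4 | 8 |
| 2 | 24 | 8 | 16 |

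The relative change does not depend on r:
- Visit 3 against baseline: (4r - 12r)/12r = -67%.
- Visit 5 against baseline: (8r - 12r)/12r = -33%.
- Visit 5 against visit 3: 8r/4r = 2, a doubling.

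**Effect of the visit windows**
- Visit 3: recall of 25 to 31 days. 25/84 - 1 = -70%; 31/84 - 1 = -63%.
- Visit 5: shortest recall 81 - 31 = 50 days, longest 87 - 25 = 62 days. 50/84 - 1 = -40%; 62/84 - 1 = -26%.
- Partner forms may be completed up to 3 days either side of the patient's visit (protocol 6.6). If that shifts both ends of the period, recall is 19 to 37 days at visit 3 (-77% to -56%) and 44 to 68 days at visit 5 (-48% to -19%).

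**How much real change is hidden.** A patient who goes from 1 to 2.5 missed days per week by visit 3 reports 2.5 × 4 = 10 days, against 12 at baseline: worse, but 2 days lower on the raw scale. The rate must exceed 12/4 = 3 times baseline before the raw count at visit 3 rises above the baseline count.

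**Alternative reading of *last assessment*.** A respondent who counts from visit 4 recalls about 28 days at visit 5, giving 28/84 - 1 = -67% there too. The doubling disappears, but the mismatch with baseline remains.

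**Check of the remedy.** Days per 28 days = count × 28/recall days. Visit 2: 12r × 28/84 = 4r. Visit 3: 4r × 28/28 = 4r. Visit 5: 8r × 28/56 = 4r. The spurious change is gone.

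**The case against.** The strongest reply is that SAP 6.4.9.4 plans no change-from-baseline analysis. SAP 6.4.9.1, 6.4.9.2, 6.4.9.3 and 6.4.9.5 each specify one by mixed model for repeated measures; this section asks only for raw descriptive data, and the endpoint wording is a general heading over several instruments. That is correct, and the -67% and -33% are not statistics that the section itself orders. But the questionnaire still sits under a change-from-baseline endpoint, and nothing else in the SAP would supply that change.

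Other limits stand in full:
- The nominal recall is the same in every arm at a given visit, so same-visit comparisons with placebo are not biased.
- The data are exploratory and untested, and the Hochberg sequence in SAP section 7 covers only the primary and secondary endpoints.
- Only the count item scales with time; chores and avoidance of plans need not.
- I could not see the forms in SAP Appendices F and G, so whether the missed-days item is a free number or banded is unknown.
- Variable recall at early withdrawal does not reach the visit columns, because SAP 4.5 keeps those data out of the by-visit sections.
- Not every e-diary variable is prorated: weekly severity in SAP 6.4.5 is a daily average. The contrast with SAP 6.1.2 concerns counts.

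A reader might infer that the table would show an early drug benefit followed by loss of effect. The documents do not support that: the same fall and rise would appear in the placebo arm, and the rise depends on how respondents understand *last assessment*.

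**Conclusion.** The point holds for the missed-days item. Followed as written, the plan yields raw counts whose within-arm change from baseline is about -67% at visit 3 and -33% at visit 5 under an unchanged burden, so the stated endpoint cannot be read from them.

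The size rests on three assumptions: a constant rate, nominal visit dates, and *last assessment* meaning the last completed questionnaire. The visit 3 figure is sensitive only to the visit windows; the visit 5 figure also depends on the third assumption.

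It would be wrong to conclude that the comparison of fremanezumab with placebo is biased, or that any confirmatory result is affected. This is a worthwhile correction to one exploratory item.

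**What to change.** In SAP 6.4.9.4:

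1. Define *last assessment* as that respondent's last completed questionnaire. This also covers a missed visit 3, after which recall at visit 5 would be about 12 weeks.
2. If the missed-days item is recorded as a number, present it also as days per 28 days: baseline count × 28/84; later count × 28/actual days since that respondent's last completed questionnaire. Use form completion dates, since a partner's form may be completed on a different day from the patient's visit. Base any change from baseline on this scale.
3. If the item is banded, show each visit with its recall period stated and give no change from baseline.

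The cost is a few lines of text and one derived variable. One weakness remains: baseline recall is still longer than later recall, and rescaling does not remove any effect of that on memory.

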6.4.9.5. Work Productivity and Activity Impairment Questionnaire: General Health V2.0

The generic version of the Work Productivity and Activity Impairment: General Health (WPAI: GH; [Appendix H](#)) questionnaire measures the overall effect of health on productivity at work and daily activities. The specific health problems version of the WPAI questionnaire allows investigators to attribute productivity and activity impairment issues to specific health conditions. Patients will complete the WPAI questionnaire in the investigational site tablet at visits 2, 3, and 5.

The scores for the following 4 domains will be derived based on the WPAI: GH questionnaire. Derived scores will be multiplied by 100 to express in percentages. Higher percentages indicate greater impairment.

1. Percent work item missed due to health: $\frac{Q2}{Q2+Q4}$
2. Percent impairment while working due to health: $\frac{Q5}{10}$
3. Percent overall work impairment due to health: $\frac{Q2}{Q2+Q4} + \left[\left(1 - \frac{Q2}{Q2+Q4} \right) \times \frac{Q5}{10} \right]$
4. Percent activity impairment due to health: $\frac{Q6}{10}$

Change from baseline at visits 3 and 5 in above calculated domain scores will be analyzed using an MMRM in a manner analogous to the analysis as described in Section 6.2.3.2. Postbaseline data will include data from visits 3 and 5. The results for overall and visits 3 and 5 will be presented.

Raw data will be summarized using descriptive statistics by visit.

